5.1.2 Additional study treatment

5.1.2.1 Pre-medication

To attenuate severity of infusion reactions, all patients in both study arms will receive the following pre-medication regimen, provided by the study center, prior to the start of the infusion (VAY736 or placebo):

- 1 h prior to infusion: Paracetamol/acetaminophen, 1000 mg orally. Adverse effects from paracetamol/acetaminophen at the listed dose are not expected.
- Directly before infusion: H1 receptor blocker e.g. dimetinden (e.g. Fenistil one to two 4 mL vials at 1 mg/mL) intravenously. Adverse effects of most H1 receptor blockers are mild and can include drowsiness and occasionally gastrointestinal disturbances, dryness of the mouth, vertigo excitation and headaches. The H1 receptor blocker used at each site is to be agreed to by Novartis before the start of the study.

5.2 Treatment arms

Patients will be randomized to one of the following 3 treatment arms, defined as:

- VAY736 active: single i.v. dose of 3 mg/kg VAY736 from infusion bag containing the active compound on Day 1
- VAY736 active: single i.v. dose of 10 mg/kg VAY736 from infusion bag containing the active compound on Day 1
- VAY736 placebo: single i.v. dose from infusion bag without active compound on Day 1

The overall randomization ratio will be 3:3:2. Before the first IA and safety review 9 patients will be randomized to the above treatments in a ratio of 2:0:1. After the safety review the remaining patients will be randomized in a ratio of 1:3:1.

Open label

Patients entering the open label cohort will be assigned to receive

- VAY736 active: single i.v. dose of 3 mg/kg VAY736 from infusion bag containing the active compound on Day 1 if blind is broken prior to the completion of the safety review
- VAY736 active: single i.v. dose of 10 mg/kg VAY736 from infusion bag containing the active compound on Day 1 if blind is broken after the completion of the safety review

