3.1 Study design

This is a non-confirmatory, randomized, partial-blind, placebo-controlled trial evaluating the efficacy, safety, pharmacokinetics of VAY736 in the treatment of patients with pemphigus vulgaris. Commercially Confidential Information

Up to approximately 32 patients will be randomly assigned in a blinded fashion to one of three single dose treatment arms, and at least 24 patients are expected to complete the study. Recruitment will be staggered and progression between doses is dependent upon a safety review milestone (see [Figure 3-1](#)).

[figure not shown]
In the pre-safety review period, 9 patients will be randomized to a single dose of either 3 mg/kg VAY736 or placebo (6 dosed with VAY736 and 3 with placebo). After dosing of these 9 initial patients, recruitment will be paused and a safety review will be conducted by an internal Data Monitoring Committee (DMC), independent from the VAY736 project team (see [Section 8.4](#)).

The DMC will review all safety data available to the 9th patient achieving Week 6. If there are no safety signals identified by this safety review, recruitment will restart into the 3 mg/kg VAY736 and placebo treatment arms, and will commence to the 10 mg/kg VAY736 treatment arm. If there is a safety signal enrollment will be put on hold, pending a full data evaluation.

Following treatment on Day 1 with study medication, standard of care (SoC) medications are to be maintained at a stable dose level with minimal dose adjustments until “disease control” in signs/symptoms of PV. “Disease control” is defined as the time at which new lesions cease to form and established lesions begin to heal (Murrell et al 2008). A protocol-defined SoC medication taper begins once a patient reaches disease control, to safely deliver the patient to the lowest dose needed to maintain control of their disease (see Section 5.5.5).

[figure not shown]
At study completion, it is intended that 9 patients will have been dosed with VAY736 at 3 mg/kg, 9 patients with 10 mg/kg, and 6 patients with placebo.

Figure 3-1 Study design: Staggered recruitment

The study will consist of the following Phases (see Figure 3-2):

Figure 3-2 Study design: Visit Schedule

Key:

B: Baseline; **R:** Randomization; **U:** unblinding of patient treatment; *****: Placebo patients may enter into open-label VAY736 treatment and restart the study at Day 1

Screening Period

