After 24 weeks in the study, at the Week 24 visit (or before in case of early withdrawal from the double-blind period that meets certain conditions – see [Section 5.5.8](#)), patients' treatment will be unblinded. When the blind is broken and a patient was assigned to placebo during the double blind period, such a patient will be offered the option to receive open label VAY736 administration from approximately one week after the Week 24 visit, and will follow the same visit pattern as if re-starting from Day 1. Patients will be assigned a new patient number for the open-label treatment. Patients joining the open label part of the study have to satisfy inclusion for active disease and safety labs as mentioned in [Section 4](#), within 2 weeks of their prior Week 24 visit. The dose of VAY736 administered will be 3 mg/kg if a patient reaches Week 24 prior

to the study safety review or 10 mg/kg if dosed after a favorable safety review by the DMC. If a patient prefers not to receive open label active treatment, they are to return within 4 weeks for their EoS visit.

For logistical reasons, it may be necessary for patients to come to the site or a hotel the evening before their scheduled assessment visit, or remain at the site following the visit (e.g. transport restrictions, long travel times from home to site). In these instances, the patients would be hospitalized at the site, but this would not be considered as an SAE.

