3.2 Rationale of study design

A randomized, placebo-controlled, partial-blind approach is used to eliminate potential bias in reporting safety and biological activity data in this study. The study will be blinded to patients, investigator site staff and the clinical trial team at the time of randomization. Unblinding of patients as they reach the end of double-blind treatment period is planned. This together with the effect of VAY736 on certain assessments may lead to members of the clinical trial team becoming inadvertently unblinded towards the end of the study period.

In addition, the study includes a staggered enrollment to allow progression between the 3 mg/kg and 10 mg/kg to be dependent upon a safety review milestone. The initial 9 patients dosed prior to the safety review will include only the 3 mg/kg VAY736 (n=6) dose and placebo patients (n=3). The rationale for this lower dose group is to confirm that the safety profile in patients with PV with regard to infusion reactions and other short term safety parameters (e.g. chemistry and hematology) is favorable, similar to that observed in study CVAY736X2101. A favorable safety review by the DMC will then enable randomization to commence into the 10 mg/kg dose group and completion of the remaining 3 mg/kg and placebo groups.

In the event that efficacy is observed with both 3 mg/kg and 10 mg/kg, the relationship between dose and parameters of clinical response (e.g., time to remission, duration of remission) can be better explored with a range of doses and exposures offered by these two dose groups.

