- It is indicated by the early safety review of the first 9 patients ([Section 3.1](#)). In the event of an unfavorable safety review, the study will not progress to dose further patients but the 9 patients will continue in the study until EoS as planned
- Other clinically significant changes or effects in the opinion of the Investigator or Sponsor that are deemed unsafe to continue dosing

In addition all blinded safety data, including events of special interest and disease specific events, will be evaluated by the Sponsor and PI continuously and at scheduled meetings. The study may be put on hold pending further data analysis, and the decision to adjust the dose or modify the pre-medication if the following criteria occur:

- The principal investigator or the Sponsor considers that the number and/or severity of AEs justify discontinuation of the study.
- Other clinically significant changes or effects in the opinion of the Investigator or Sponsor that are deemed unsafe to continue dosing.

The study can also be terminated at any time for any reason by Novartis. Should this be necessary, the Investigator will be informed of the procedures to be followed to assure that adequate consideration is given to the protection of the patient's interests. The Investigator will be responsible for informing IEC / IRB's of the early termination of the trial.

Individual subject withdrawal

Due to the single dose nature of the study, no individual treatment stopping rules are provided. Patients may voluntarily withdraw from the study for any reason at any time. They may be considered withdrawn if they state an intention to withdraw, fail to return for visits, or become lost to follow-up for any other reason.

If a patient withdrawal occurs for any reason, the investigator must make every effort to determine the primary reason for a patient's withdrawal from the study and record this information on the CRF.

Patients that become pregnant during the study should be followed up as per the assessment schedule. The investigator may determine whether any assessments should not be performed if they are considered to not be clinically appropriate, in conjunction with the patients' treating physician/obstetrician.

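### Protocol Sections 5.2 and 3.1 set the open-label dose by different triggers, and Section 5.5.11 does not settle what happens after an unfavourable safety review

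*Protocol*

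**What the plan says.** Two sections of the protocol assign the open-label dose.

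- **Section 5.2, Open label.** The dose is 3 mg/kg "if blind is broken prior to the completion of the safety review" and 10 mg/kg "if blind is broken after the completion of the safety review". The outcome of the review is not mentioned.
- **Section 3.1, Open label administration.** "The dose of VAY736 administered will be 3 mg/kg if a patient reaches Week 24 prior" to the review, "or 10 mg/kg if dosed after a favorable safety review by the DMC". No dose is stated for a patient dosed after an unfavourable review.

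Three other provisions bear on it.

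- **Section 3.2**, on the randomised part: "A favorable safety review by the DMC will then enable randomization to commence into the 10 mg/kg dose group".
- **Section 3.1**, on a signal at the review: "If there is a safety signal enrollment will be put on hold, pending a full data evaluation". This speaks of enrolment and does not mention open-label dosing.
- **Section 5.5.11, stopping rules.** If any listed criterion is met, the study stops and dosing halts until a full safety review has been done. An adverse early review of the first nine patients is one of the criteria. In that event "the study will not progress to dose further patients but the 9 patients will continue in the study until EoS as planned".

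Section 5.5.13.1 withdraws the open-label offer if the study is terminated.

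**The concern.** The safety review exists to decide whether the trial may move from 3 to 10 mg/kg. For the randomised part, Section 3.2 makes a favourable outcome the gate. For the open-label part, Section 3.1 has that gate and Section 5.2 does not. Section 5.2 is where the treatment arms are defined, so a site or pharmacist may well work from it.

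The sections also look at different dates. Section 5.2 uses the day the blind is broken. Section 3.1 uses reaching Week 24 for one dose and the day of dosing for the other. A patient whose unblinding and infusion fall on either side of the review can therefore be classified differently by the two sections.

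At stake is the dose given to individual former placebo patients from the first nine, and whether any open-label dose may be given after an unfavourable review.

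**Working it through.** The plan states no figure on this point, so the check is a comparison of wording plus simple arithmetic on timing.

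**Each case under the two dosing sections**

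| Placebo patient | Section 5.2 | Section 3.1 |
|---|---|---|
| Unblinded at Week 24 and dosed, both before the review | 3 mg/kg | 3 mg/kg |
| Unblinded at Week 24 before a favourable review, dosed after it | 3 mg/kg | both conditions met |
| Unblinded early (Section 5.5.8) and dosed, both before the review | 3 mg/kg | neither condition met |
| Unblinded early before a favourable review, dosed after it | 3 mg/kg | 10 mg/kg |
| Unblinded after a favourable review | 10 mg/kg | 10 mg/kg |
| Unblinded after an unfavourable review | 10 mg/kg | no dose stated |

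The sections agree in the first and fifth rows only. The fourth row is the one outright conflict between two stated doses. In the second row the ambiguity lies inside Section 3.1. The early-unblinding rows are clearest for a patient unblinded at Week 12. After a second increase in standard of care later than Week 12, Section 5.5.8 brings the Week 24 assessments forward, and Section 3.1 does not say whether that counts as reaching Week 24.

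**The last row against Section 5.5.11.** The opening of the stopping rules halts dosing and exempts nobody, which points to no infusion. The bullet on the early review then contrasts further patients with the nine, who carry on as planned. The plan for a placebo patient includes the open-label offer: the synopsis, footnote 17 of the assessment schedule and Section 5.5.12 all state it without reference to the review's outcome. Section 5.5.13.1 does not resolve this, because it applies on termination and the bullet describes continuation to the end of study.

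**Who can be affected**

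- The first nine comprise 6 on VAY736 and 3 on placebo (Section 3.1).
- After an unfavourable review no other patients exist. Recruitment pauses until the review is done, so anyone unblinded before it also belongs to the first nine. Either way the ceiling is 3.

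**When unblinding falls relative to the review**

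Let g be the weeks by which a placebo patient was dosed before the ninth patient, and r the weeks from the ninth patient's Week 6 to completion of the review. Neither accrual nor r is given in the documents, so r is an assumption.

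- Routine unblinding precedes the review if 24 < g + 6 + r, that is g > 18 − r. With r = 0 this is g > 18; with r = 4, g > 14.
- If all nine are dosed within 18 weeks and r = 0, all 3 placebo patients are unblinded after the review and fall under the 10 mg/kg bullet of Section 5.2 whatever it finds.
- The second row of the table needs the review to finish between Week 24 and the infusion about one week later (Section 3.1): 18 − r < g < 19 − r, a one-week slot.
- Unblinding at Week 12 precedes the review if 12 < g + 6 + r, that is g > 6 − r. With r = 0 this is g > 6.

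**The case against.** The strongest reply is that Section 5.2 should not be read alone. A reader might infer that the protocol directs 10 mg/kg after an unfavourable review, and the documents do not support that. Section 5.5.11 halts dosing, not merely enrolment, once an adverse early review triggers the stop. Its natural sense covers an open-label infusion. Continuing as planned can fairly be taken to mean continued follow-up, since a placebo patient who declines the infusion has an end-of-study route in Section 3.1. Nothing states that 10 mg/kg follows an unfavourable review; Section 5.2 simply omits the outcome.

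This part of the reply stands, and it reduces the point from an instruction to a conflict with a partial safeguard. It does not remove the conflict. Section 5.5.11 never mentions the open-label infusion, it separates the nine from further patients, and Section 3.4 says the offer is meant to give every participant a fair chance of receiving the drug.

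A reader might also infer that any patient unblinded before the review and dosed after it receives different doses under the two sections. That is too strong. A patient routinely unblinded at Week 24 meets the 3 mg/kg condition in both sections, and after a favourable review also meets the 10 mg/kg condition of Section 3.1. Two clearly different doses arise only with early unblinding under Section 5.5.8.

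Finally, the numbers are small and the open-label part has no bearing on the primary comparison. Both are true.

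**Conclusion.** The point holds as an inconsistency between operative dosing provisions. Sections 5.2 and 3.1 differ in trigger date and in whether the review's outcome matters, and Section 5.5.11 only partly covers the unfavourable case. The protocol as a whole does not clearly direct 10 mg/kg after an unfavourable review, nor does it clearly rule out the open-label infusion then.

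The size is at most the 3 placebo patients among the first nine. In the unfavourable-review case each would also have to meet the open-label criteria in Section 4 (PDAI above 10, stable standard of care, blood counts within limits) and accept the offer. The timing cases depend on accrual and on the duration of the review, which the documents do not give. The Week 12 comparison is not affected. The matter should be corrected because it concerns which dose a patient may receive and the correction is cheap.

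**What to change.** Reconcile Sections 3.1, 5.2 and 5.5.11 so that they share:

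- one trigger date for the open-label dose, worded to cover patients unblinded early under Section 5.5.8 as well as those unblinded at Week 24;
- one stated condition on the outcome of the safety review;
- an explicit statement of whether the open-label offer to the placebo patients among the first nine stands after an unfavourable review, cross-referenced to Section 5.5.13.1.

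Which dose rule applies is for the sponsor to decide. The cost is a protocol wording change through the usual amendment route, with no effect on sample size, visits or the analysis of the primary variable.

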5.3 Treatment assignment

Randomization numbers will be assigned in ascending, sequential order to eligible subjects (see [Section 5.5.1](#) for details). The investigator will enter the randomization number on the CRF.

The randomization numbers will be generated using the following procedure to ensure that treatment assignment is unbiased and concealed from subjects and investigator staff. A randomization list will be produced by or under the responsibility of Novartis Drug Supply Management using a validated system that automates the random assignment of treatment arms to randomization numbers in the specified ratio. The randomization scheme for subjects will be reviewed and approved by a member of the Novartis IIS Randomization Group. Numbers

between 5101 and 5112 will be used before the safety review. Numbers between 5113 and 5132 (or higher) will be used after the safety review.

Randomization Procedure for central management of randomization numbers:

When an eligible patient at a participating study site is ready to be randomized into the study, the steps below will be followed:

1. The site designee will complete a Randomization Request form and fax or email to the Novartis designee.
2. On receiving, the Novartis designee will write the next available randomization number within the randomization list for the corresponding part of the study on the form and fax or email back.
3. On receiving the allocated randomization number, the unblinded pharmacist or authorized designee will use the information on the completed form to ensure that the patient receives the correct study medication, according to the provided randomization list.
4. After inclusion of each new patient, the site designee will countersign the Randomization Request form, and fax or email it back to the Novartis designee to document the correct assignment of the patient's randomization number and the date the patient received their first dose of study medication.

The site designee will enter the randomization number on the CRF.

5.4 Treatment blinding

This is a partial blind study: subjects, investigator staff, persons performing the assessments, and data analysts will remain blind to the identity of study treatments at the time of randomization and during the double-blind treatment period according to the specifications provided in [Appendix 4](#). Randomization data are kept strictly confidential until the time of unblinding for the respective person(s) with the following exceptions:

- The pharmacist charged with preparing and distributing infusion solutions containing VAY736 or placebo
- The medical monitor/Investigator at the site, independent to the study, who will review the hematology panel including differentials results throughout the study
- The unblinded monitor source data verifying the hematology panel and monitoring drug accountability

The PK bioanalyst will be unblinded during the clinical study, but will not provide individual PK data prior to data-base lock, except in case of an interim analysis happening after all patients have completed Week 24 and all team members, investigators and patients have been unblinded.

In order to help reduce the risk of unblinding that might arise if an infusion reaction occurs, all patients will receive treatment with paracetamol/acetaminophen and a H1 receptor blocker prior to infusion with VAY736.

An unblinded pharmacist at the investigator site will prepare the study treatment for infusion from the bulk open-labeled supplies. The diluent (dextrose 5% in water solution) serves as placebo and will not contain VAY736.

the hematology laboratory evaluation results will be concealed from the Investigators and patients in order to maintain the study blind. The necessary safety review may lead to the Novartis study team being inadvertently unblinded, however this information will not be communicated to the investigator.

Investigators and patients will be unblinded to treatment assignment after Week 24 (or earlier see [Section 5.5.8](#)) visit in order to propose open-label administration of VAY736 to the placebo arm.

Further unblinding will only occur in the case of subject emergencies (see [Section 5.5.12](#)), at the time of the interim analysis and at the conclusion of the study.

Further information regarding blinding (and unblinding) is presented in [Appendix 4](#).

5.5 Treating the subject

5.5.1 Subject numbering

Screening number

Each subject screened is assigned a unique screening number. The screening number is a combination of the center number that is provided by Novartis, and a five digit number starting with 00001 for each subject which is assigned by the Investigator. Therefore, if the center number is 1001 the screening numbers will be assigned such as 100100001, 100100002, 100100003 in ascending order. If the center number is 1002, the screening numbers will be 100200001, 100200002, 100200003 in an ascending order.

Randomization / treatment number

If the patient is deemed eligible for the study and will commence dosing, a randomization number will be assigned. Once assigned to a patient, a randomization number will not be reused.

The randomization number becomes the definitive subject number as soon as a patient receives the first dose of the respective study treatment.

There should be a source document maintained at the site which links the screening number to the randomization assignment number (once assigned). This source document should be provided to all appropriate parties (i.e. Central Laboratory, ECG Laboratory) as soon as this is available.

Randomization numbers will be generated for 32 (or more) to allow for approximately 24 subjects to complete the study. Subjects will be assigned randomization numbers, 5101-5132. Numbers between 5101 and 5112 will be used before the safety review. Numbers between 5113 and 5132 (or higher) will be used after the safety review.

Placebo patients entering the open-label part cohort will be issued with a new randomization number. These patients will be assigned randomization numbers, 7101-7130. If a patient joins the open-label VAY736 part, the new randomization number assigned will correspond to the original randomization number (e.g. patient 5103 would be assigned 7103).

The table below summarizes the general details of the numbering of the patients once randomized to treatment:

Table 5-2 Patient Numbering

Part	Randomization Number
Single dose (pre-safety review)	5101 – 5112
Single dose (post-safety review)	5113 – 5132 (or higher)
Open label	7101 – 7132 (or higher)

